8.2 SAFETY ASSESSMENTS

To monitor the safety of student participants, AEs and SAEs will be monitored at each treatment and assessment visit. For treatment visits, study counselors will document any new AEs/SAEs spontaneously reported during therapy sessions. Unsolicited events that meet the definition for AEs or SAEs (see sections 8.3.1 and 8.3.2) will prompt further inquiry by the

research team to ascertain onset, severity, relatedness to treatment, outcome, and measures taken to address AE or SAE, if any.

During each assessment visits, AEs and SAEs will also be assessed and monitored through general inquiry by the IEs. During remote assessments, IEs will first inquire as to where the participant is physically located. IEs will also implement the University of Washington Risk Assessment Protocol (UWRAP)¹¹⁰ at each assessment to monitor suicide risk more closely.

The following specific steps will be taken:

- 1) The first step in managing risk during and following assessments with suicidal and other highly distressed or volatile student participants is to assess the participant's mood before the assessment starts. To this end, the IE administers the UWRAP pre-assessment questions at the beginning of each assessment session which assesses the student participant's level of stress and urges to suicide, self-harm, or use substances at the beginning of the assessment. The IE uses this information in structuring and pacing the assessment to the subject participant's tolerance.
- 2) At the first assessment meeting (and reviewed thereafter as needed), the IE begins the UWRAP Mood Improvement Protocol. Two items are used to determine strategies the student participant can use to manage any distress caused by the assessments.
- 3) At the end of each assessment session, the IE administers the UWRAP Debriefing Form, which asks about the student participant's mood, stress, and urges at that point. Thus, the IE can tell how the student participant's mood has changed during the session.
- 4) An Imminent Suicide Risk and Serious Self-Injury Form must be completed if the student participant rates suicidality higher than 4 on a 7-point scale or states that he/she is uncertain about being able to control suicidal impulses.
- 5) If suicide risk is moderate to high, the IE implements the necessary Suicide/Distress Intervention Protocol for Assessors. In these instances, IEs must also call the site PI (or his/her designee) to review the suicide risk assessment and intervention.
- 6) The Debriefing Form lists the strategies for responding to suicidal risk and those used should be checked off and described, if necessary.
- 7) At the end of the assessments, IEs offer and engage student participants in mood improvement activities according to the Mood Improvement Protocol. If there is not high risk, the IE then closes the assessment, works with the student participant to improve his/her mood, and sends the student participant home (if in person) or ends the videocall (if remote). The IE then makes a mood improvement rating for the student participant.
- 8) At the end of each assessment, IEs provide student participants with crisis resources and emergency phone numbers.

8.3 ADVERSE EVENTS AND SERIOUS ADVERSE EVENTS

8.3.1 DEFINITION OF ADVERSE EVENTS

An Adverse Event (AE) is any untoward medical occurrence in a study subject that does not necessarily have a causal relationship with this treatment.

An AE therefore can be any unfavorable and unintended sign (including laboratory finding), symptom or disease temporally associated with participation in an investigational study, whether or not considered intervention-related. In addition to new events, any increase in the severity or frequency of a pre-existing condition that occurs after the subject signs a consent form for participation is considered an AE. This includes any side effect, injury, toxicity, or sensitivity reaction.

Any condition, laboratory abnormality, or physical finding with an onset date prior to the subject signing consent for study participation is considered pre-existing in nature and part of the subject's medical history and will not be recorded as an AE.

In this study, we will classify the following as Adverse Events (AEs):

- Breach of confidentiality.
- Evidence of coercion to participate.
- Evidence of distress during assessments (as indicated by a score of >5 on item 2 of the UWRAP Debriefing Form *and* an increase of at least one point on this same item when compared to the UWRAP Pre-Assessment).
- Significant increase in suicidal ideation (as measured by a CGI-I score of 6 or 7, which is completed weekly by counselors following session 4 and at each assessment point by the IEs).

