1.3 SCHEDULE OF ACTIVITIES

All participants will self-refer to an initial appointment (i.e., intake) at their CCC, and as part of standard operating procedures will meet with an intake counselor, either in-person or remotely following practices of the CCC, as a first step to access CCC services. As part of the CCC's standard clinic workflow, all students seeking services will complete the Counseling Center Assessment of Psychological Symptoms (CCAPS-62). Students who meet inclusion and exclusion criteria will be given a brief explanation of the study by the intake counselor. Interested students will be scheduled for an appointment conducted either in-person or remotely with a member of the research who will review the consent form with each student. Students who sign the consent form will then complete a baseline assessment with the Independent Evaluator (IE), either online or in-person.

The schedule of activities for the CAMPUS Trial is presented in Table 1 on the next page.

Table 1. Schedule of Activities for the CAMPUS Trial

	-1	0	Stage 1						Stage 2						26
			1	2	3	4	5	6	7	8	9	10	11	12	13
Completed by CCC Intake Counselor															
Screening Data Form*		X													
Completed by Student Participants															
Demographic Information			X												
Sexual Orientation and Gender Identity		X													
Counseling Center Assessment of Psychological Symptoms (CCAPS)	X	X	X	X	X	X	X	X	X	X	X	X	X	X	X
Clinical Global Impression – Severity (CGI-S)		X			X			X			X				X
Clinical Global Impression – Improvement (CGI-I)					X			X			X				X
Adverse Events and Serious Adverse Events (AE/SAE)		X	X	X	X	X	X	X	X	X	X	X	X	X	X
Difficulties in Emotional Regulation Scale (DERS)		X						X			X				X
DBT Ways of Coping Checklist (WCCL)		X						X			X				X
Acceptance and Action Questionnaire (AAQ)		X						X			X				X
Suicide Cognitions Scale (SCS)		X			X			X			X				X
Self-Efficacy for Managing Emotions		X			X			X			X				X
Optimism Hope Scale (OHS)		X			X			X			X				X
Personality Assessment Inventory-Borderline Features Scale (PAI-BOR)		X													
Life Stressor Checklist-Revised (LSC-R)		X													X
Drug Abuse Screening Test (DAST)		X													X
Alcohol Use Disorders Identification Test (AUDIT)		X													X
Student Treatment Credibility Questionnaire (STCQ)				X					X						
Student Treatment Expectations Questionnaire (STEQ)			X						X						
Client Satisfaction Questionnaire (CSQ)								X							X
Academic Functioning		X													X

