Completed by Independent Evaluators															
University of Washington Risk Assessment Protocol (UWRAP)			X			X			X			X			X
Clinical Global Impression – Severity (CGI-S)		X			X			X			X				X

Table 1. Schedule of Activities for the CAMPUS Trial

	-1	0	Stage 1						Stage 2						26	
			1	2	3	4	5	6	7	8	9	10	11	12	14	
Clinical Global Impression – Improvement (CGI-I)					X			X			X				X	X
Scale for Suicidal Ideation (SSI)		X		X			X			X		X			X	X
Self-Injurious Thoughts and Behaviors Interview (SITBI)	X						X			X			X		X	X
Global Assessment Scale (GAS)		X		X			X			X		X			X	X
Treatment History Interview (THI)	X														X	X
Completed by Research Staff																
Informed Consent		X														
Inclusion/Exclusion Checklist		X														
CAMS Rating Scale-3 ¹																
DBT Adherence Rating Scale ¹																
Completed by Counselor Participants																
Reveal Randomization			X						X							
Demographic Information Form (DIF) ²		X														
Treatment Compliance Item*			X	X	X	X	X	X	X	X	X	X	X	X	X	
AE/SAE Summary Form			X	X	X	X	X	X	X	X	X	X	X	X	X	
Clinical Global Impression – Severity (CGI-S) ³			X					X								X
Clinical Global Impression – Improvement (CGI-I)				X	X	X	X	X	X	X	X	X	X	X	X	
Treatment Assignment Reaction Form		X							X							
Counselor Treatment Expectations Questionnaire (CTEQ)		X							X							
Client Satisfaction Questionnaire-Counselor (CSQ-C) and Counselor Satisfaction Rating ³								X								X
Reasons for Termination Checklist ³								X								X
TAU Questionnaire ³									X							
Counselor Telehealth Questionnaires (CTSQ) ³																X
Zero Suicide Workforce Survey- Abbreviated (ZSWS) ⁴	X															X
Focused Interview ⁵																X

Table 1. Schedule of Activities for the CAMPUS Trial

	Stage 1						Stage 2									
	-1	0	1	2	3	4	5	6	7	8	9	10	11	12	13	14
Notes (1): 1. Research staff will complete this measure on a random sample of therapy sessions. 2. Counselor participants will complete this measure once when they enter the study. 3. Counselor participants will complete this measure following students' last treatment session which may be earlier than Week 14. 4. Counselor participants will complete this measure at the start of their participation in the study and then every six months. 5. Counselor participants will complete this interview at the end of their participation in the study.																

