Notes (2): \$For all assessments collected as part of an Independent Evaluator (IE) visit (i.e., those assessments not collected specifically at treatment visits), there will be a +/-1 week window around the scheduled assessment date for purposes of data collection. IE assessments collected outside of this window will still be collected and values will be imputed based on when the assessment should have occurred.																
Notes (3): *These measures are exclusively collected in the Titanium electronic medical record and will be exported at regular intervals throughout the study period.																

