4.2 OVERALL DESIGN

As shown in Figure 1 (on page 9), the proposed multisite SMART will involve randomization at two stages. At Stage 1, all student participants ($N = 480$) will be randomized to 4-6 weeks of CAMS or TAU. Beginning at session 4, the counselor will rate the student participant in terms of clinical response. Insufficient responders (e.g., non-responders) to Stage 1 will be re-randomized to one of two Stage 2 treatments for an additional 1-8 weeks: 1) CAMS (either continued or for the first time) or 2) CC-DBT.

Thus, four ATSSs are possible:

- ATS-1: Start with CAMS, if responding, enter maintenance treatment; if not, continue with CAMS;
- ATS-2: Start with CAMS, if responding, enter maintenance treatment; if not, switch to CC-DBT;
- ATS-3: Start with TAU, if responding, enter maintenance treatment; if not, switch to CAMS;
- ATS-4: Start with TAU, if responding, enter maintenance treatment; if not, switch to CC-DBT.

Our pilot showed at Stage 1, 48% and 44% treatment response rates across CAMS and TAU, with 27% and 17% attrition rates, respectively—differences not statistically significant. Based on these findings, we assume an equal response rate of 50% across both Stage 1 treatments (CAMS and TAU), leaving $N=240$ participants eligible for Stage 2 treatments. Treatment responders at the end of Stage 1 will end study treatment and enter maintenance, which includes monthly monitoring and continued assessments with the IEs. All student participants will complete weekly measures as part of treatment. Research assessments by independent evaluators (IEs) will be conducted at baseline, mid-Stage 1 (Week 3), end of Stage 1 (Week 6), mid-Stage 2 (Week 10), end of Stage 2 (Week 14), and at 3-month follow-up (Week 26).

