6.1.5 STUDY INTERVENTION DESCRIPTION

Study interventions include Treatment as Usual (TAU), the Collaborative Assessment and Management of Suicidality (CAMS), or CC-DBT.

TAU: Treatment as Usual consists of normal College Counseling Center (CCC) therapeutic procedures. TAU will allow counselors to determine level of care and therapeutic modality depending on the needs of the participant.

CAMS: CAMS is an evidence-based, suicide focused approach⁶¹ that was first developed and studied in a CCC specifically for college students.⁶² CAMS is a problem-focused treatment that targets client-defined suicidal “drivers” or issues that lead to SI.⁷ Central to CAMS is the use of the Suicide Status Form (SSF), a multipurpose clinical assessment, treatment planning, tracking, and outcome tool.⁷ The SSF serves as a clinical roadmap to guide collaboration as counselor and client sit next to each other exploring SR through quantitative/qualitative assessments and suicide-specific treatment planning. All CAMS sessions begin with a consideration of the “SSF Core Assessment.” Sessions then focus on the CAMS Stabilization Plan (CSP) and the client’s suicidal drivers. All sessions end by updating the CSP and problem-focused care targeting suicidal drivers. CAMS is theoretically agnostic; counselors use their own approach to treating client-identified suicidal drivers.

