8 STUDY ASSESSMENTS AND PROCEDURES

8.1 ENDPOINT AND OTHER NON-SAFETY ASSESSMENTS

We have divided measures into demographics, primary and secondary dependent variables (DVs), mediators, moderators, and implementation/process variables. Measures were selected if they: 1) fit the study aims, 2) have adequate psychometrics, 3) are listed as Common Data Elements in NIH or have been used in previous SR studies, 4) have shown sensitivity to change, 5) have been used with college students, 6) map onto the RDoC categories (Negative Valence Systems, Positive Valence Systems, Cognitive Systems, Social Processes, and Arousal and Regulatory Systems),⁷⁹ 7) are directly relevant to the application of CAMS or DBT, and 8) allow for reduced burden to student participants—the latter in response to reviewers' concerns.

Demographic Variables.

With student participants' consent, age, marital status, family income, residence, GPA, race, year in school, major, ethnicity, sexual orientation, cultural identity, and gender identity will be obtained via EMR/the registrar or by completing the Demographic Information Form at baseline.

SMART Primary Tailoring Variable: Sufficient vs. Insufficient Response to Stage 1 Treatments. Unique to SMARTs are tailoring variables or variables upon which subsequent randomizations are based.⁵⁹ For this trial, sufficient treatment response will be the primary tailoring variable and assessed by the Clinical Global Impressions (CGI),¹⁰³ adapted to SR. As noted in Preliminary

Studies, the CGI, adapted to SR, showed high inter-rater reliability and construct validity; this fits with other studies demonstrating that non-blinded trained counselors typically can offer CGI ratings commensurate to blinded IEs.¹¹¹

In SMARTs, a tailoring variable is a tool for clinical decision-making, in this case deciding on response to treatment, and therefore it will be based on clinical assessments by providers (and not the IE).⁵⁹ Beginning at session 4 and following each subsequent session, the counselor will complete the 7-point Likert-style CGI developed in the CAMPUS feasibility study to rate overall improvement in SR since baseline from (1) “*Very much improved*” to (7) “*Very much worse*.” Sufficient response will be defined as an Improvement score of ≤ 2 (“*Much improved*” or “*Very much improved*”).

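### Under the text, the CGI-I-based worsening AE has no scheduled counselor rating in sessions 1-3, while Table 1 appears to schedule one earlier

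*Combined protocol and SAP*

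**What the plan says.** Three places in the text agree on when the counselor CGI-I begins.

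- Section 4.2: "Beginning at session 4, the counselor will rate the student participant in terms of clinical response".
- Section 8.1, on the tailoring variable: "Beginning at session 4 and following each subsequent session, the counselor will complete the 7-point Likert-style CGI". A score of 2 or less counts as sufficient response.
- Section 8.3.1 lists a significant increase in suicidal ideation as an AE, measured by a CGI-I of 6 or 7, "completed weekly by counselors following session 4 and at each assessment point by the IEs".

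The first evaluator assessment after baseline is at Week 3 (4.2), and Notes (2) to Table 1 say "there will be a +/-1 week window around the scheduled assessment date".

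Table 1 (section 1.3) has a weekly row for the counselor CGI-I. As it reads in the text copy, the row starts at Week 2, one column after the counselor row "AE/SAE Summary Form", which starts at Week 1.

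**The concern.** Worsening of symptoms, including suicidal thoughts, is the first risk listed in section 2.3.1, and 8.3.1 turns it into a named AE with a numeric criterion. A criterion can only be met when the scale is scored. If counselors first score it at session 4, then for the first three sessions the criterion depends on a single evaluator visit, which the window allows to fall as late as Week 4. A student who leaves before session 4 never receives a counselor CGI-I under the text.

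The text and the schedule also appear to give different instructions about the same form. What is at stake is how completely, and how uniformly, one named AE is picked up early in treatment. Section 8.3.5 sends all AEs to the DSMB three times a year.

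**Working it through.** The plan states no figure to reproduce. The check compares the text with Table 1 and counts ratings.

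**Step 1: ratings under the text.** Sessions are prescribed weekly (6.1.6), so session number roughly equals week number. Stage 1 runs 4 to 6 weeks. A student with six sessions gets counselor ratings at sessions 4, 5 and 6, which is 3. A student who stops at the four-session minimum (synopsis) gets 1.

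**Step 2: where the Table 1 row starts.** In the text copy the counselor CGI-I row has 12 consecutive marks and an empty last cell (Week 26). The header on that page runs 1 to 12 and then 14. With Week 13 restored, a Week 2 start would give 13 marks. A Week 4 start gives at most 11 marks (Weeks 4-14), or 10 under the printed header. On either basis the row is longer than a Week 4 start allows, and it has one mark fewer than the weekly AE/SAE Summary row.

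Two cautions apply.

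- Some marks look displaced. The counselor expectations questionnaire falls in column 0, although 8.1 puts it after the first session. The TAU Questionnaire falls in Week 7, although 8.1 puts it at the end of Stage 1.
- Some counts look wrong. The SSI and GAS rows show 7 marks, although 4.2 gives six evaluator occasions. The UWRAP row shows 5, although 8.2 requires it at every assessment.

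An early start is therefore likely, with Week 2 the best reading and Weeks 1 to 3 the plausible range.

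**Step 3: the difference.** The last column is the per-student difference times 480.

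| Table 1 start | Six sessions: table vs text | Four sessions: table vs text | Maximum over 480 students |
|---|---|---|---|
| Week 1 | 6 vs 3, 3 fewer (3/6 = 50%) | 4 vs 1, 3 fewer (3/4 = 75%) | 3 x 480 = 1,440 |
| Week 2 | 5 vs 3, 2 fewer (2/5 = 40%) | 3 vs 1, 2 fewer (2/3 = 67%) | 2 x 480 = 960 |
| Week 3 | 4 vs 3, 1 fewer (1/4 = 25%) | 2 vs 1, 1 fewer (1/2 = 50%) | 1 x 480 = 480 |

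These are counts of forms and assume that every student attends the early sessions. They are not counts of missed events.

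**Step 4: what covers sessions 1 to 3 without the counselor CGI-I.**

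- One evaluator visit at Week 3 +/- 1, that is Weeks 2 to 4, with CGI-I, UWRAP and active AE inquiry, in both arms (4.2, 8.2, Table 1).
- The CCAPS at every session, with no stated action threshold for worsening (8.1).
- The counselor AE/SAE form and the student AE/SAE row in Table 1. At treatment visits counselors record unsolicited events (8.2, 8.3.4).
- Weekly staff or case management meetings at each center (2.3.3).
- In the CAMS arm only: "All CAMS sessions begin with a consideration of the" SSF Core Assessment (6.1.5).
- The general rule that any deterioration is an AE (8.3.1, 8.3.4), and SAE capture, which does not use the CGI-I (8.3.2).

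**The case against.** The strongest reply is that session 4 is a deliberate choice. Three sections agree on it, and 4.4 ties early re-randomization for worsening on the counselor CGI-I to the period after session 4. On that view only the Table 1 row needs correcting. This stands as far as consistency goes: correcting the table alone would remove the contradiction. It would not give the named AE a counselor rating in the first three sessions.

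A reader might infer three stronger things, and the documents support none of them.

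- *Early worsening goes unmonitored.* Step 4 shows that it does not. The gap concerns one scheduled counselor rating for one named AE.
- *Table and text cannot be reconciled.* That would need reliable mark counts. Other rows of the same table have counts that do not match the text, so a mismatch is likely but not proven.
- *Comparisons between Stage 1 arms or sites are compromised.* Section 9 plans no between-arm or between-site comparison of AEs, and the evaluator-rated SSI at Week 3 gives a view of early change in both arms. Nothing shows that sites choose their own schedule: the Data Center builds the electronic forms centrally (10.1.9.1), and the manuals of procedures are not available here.

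It is also fair to say that an added counselor rating would not remove the difference in what CAMS and TAU counselors know about a student's suicidality. Both are unblinded, and only CAMS prescribes a structured suicide assessment at each session. The case for the change is a scheduled rating in both arms, not equal detection.

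**Conclusion.** The point holds as a modest gap in safety ascertainment together with a likely inconsistency between text and table. Under 4.2, 8.1 and 8.3.1, the CGI-I criterion for increased suicidal ideation can be met before session 4 only through the one evaluator rating around Week 3. Table 1 very likely schedules the counselor rating earlier.

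Taking Week 2 as the start, the text gives two fewer counselor ratings per student. This assumes weekly sessions and full early attendance. How many worsening events would be missed cannot be estimated from the documents. The primary endpoint, the power figures, the tailoring rule and the planned analyses are unaffected. Confidence is medium because the table is damaged in the copy reviewed; the row should be checked against the original.

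**What to change.** Amend 8.1 and 8.3.1 so that counselors complete the CGI-I after each session from session 2 for AE detection, with a 6 or 7 counting as the AE. State separately that its use as the tailoring variable (score of 2 or less) begins at session 4, so the response rule does not change. Align the counselor CGI-I row in Table 1 with that wording. Session 1 can reasonably be left out: the scale rates change since baseline, and the first appointment is typically within 7 days of the baseline visit (6.1.3).

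The cost is wording in three places and a one-item rating at sessions 2 and 3, at most about 2 x 480 = 960 ratings, which Table 1 already appears to schedule. The downside is a little more counselor time and somewhat more recorded AEs. If the sponsor prefers to keep session 4, the minimum is to correct Table 1.

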8.3.2 DEFINITION OF SERIOUS ADVERSE EVENTS

A Serious Adverse Event (SAE) is any adverse event occurring during the study or within 30 days of termination of the subject from the study that results in one or more of the following outcomes:

- Suicide death
- Non-suicide death
- Suicide attempt (not death) with non-zero intent to die
- Inpatient Hospitalization (specify below)
 - Suicidal ideation
 - Non-suicidal self-injury (NSSI)
 - Other mental health event (e.g., depression, homicidal ideation, anxiety)
 - Other non-mental health event (excludes scheduled hospitalizations for non-acute, unrelated cause such as an elective surgery)
- Emergency Department (ED) visit, not resulting in inpatient hospitalization (specify below)
 - Suicidal ideation
 - Non-suicidal self-injury (NSSI)
 - Other mental health event (e.g., depression, homicidal ideation, anxiety)

